  -  All subjects should have screening thoracic and abdominal CT angiograms with complete visualization of both iliacs, femorals, and aorta (and subclavian/axillaries, if applicable), up to and including the aortic annulus
  -  In addition to the protocol required assessment (NIHSS and MMSE); for subjects with neurological event or stroke, additional NIHSS and MMSE exams are to be performed at 30 days and 90 days post-event. mRS should be completed at 7 days post-event or discharge (whichever occurs first), 30 days, and 90 days post-event. NIHSS is also to be done within 24 hours of any aortic valve or ascending aortic intervention
  -  NIHSS to be done within 24 hours post- procedure
  -  Additional Neurological Assessments include: Visual Fields Testing, Gait Assessment, Hand Function, Writing Evaluation, and Drawing Assessment
  -  SAE, MAE, cardiovascular events, device-related events, including device-related technical observations, UADEs, USADEs, all stroke (CVAs), and death reports
  -  Use of relevant medications (diuretics, aspirin, anticoagulants, ACE-I, ARB, beta-blockers, statins and anti-platelets)
  -  Quality of Life Questionnaires collected at baseline may be administered any time after the subject has provided informed consent but should be collected prior to informing the subject of randomization assignment
  -  Quality of Life Questionnaire – EQ-5D to be administered via telephone. SF-36 will also be collected in selected geographies, refer to **Appendix R.12**

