#### C.5.1.4 Major Adverse Event

Major adverse event (MAE) includes:

- MACCE
- Acute kidney Injury
- Cardiac tamponade
- Prosthetic valve dysfunction
- Cardiogenic shock
- Prosthetic valve endocarditis
- Life-threatening, disabling or major bleeding
- Major vascular complication
- Cardiac perforation
- Valve malpositioning

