### *C.5.2 Reporting*

Investigators are required to keep records on “all relevant observations, including records concerning adverse device effects (whether anticipated or unanticipated)” [21 CFR 812.140; ISO 14155 (2011)]. Adverse event collection will begin from the point of trial enrollment to trial closure. All new or worsening (from baseline) adverse events and technical observations will be captured on the AE eCRF through the 24-month follow-up visit. It is the responsibility of the Investigator to assess the subject for adverse events and capture the required adverse event information on the AE eCRF.

Once a subject has completed their 24-month scheduled follow-up visit only serious adverse events, major adverse events, cardiovascular events, device-related adverse events, including device related technical observations, unanticipated adverse device effects (UADE) or unanticipated serious adverse device effects (USADE), all strokes (CVAs) and deaths will be required to be reported. Reference section C.5.1 Adverse Events for event definitions and criteria. Medtronic representatives or their designees will conduct monitoring visits to review source documentation and verify the complete and accurate capturing of adverse events.

The Investigator must also notify the responsible IRB/MEC regarding new and significant safety information and any event identified by Medtronic that requires expedited FDA, and/or local regulatory agency, reporting as serious, unexpected, and related to the investigational device. It is the responsibility of the investigator to ensure site specific IRB/MEC safety reporting requirements are met.

Medtronic Clinical will ensure all device-related adverse events and all procedure-related SAEs are processed according to internal policies and procedures. When necessary, Medtronic Field Assurance will respond to sites in writing with the findings related to the product experiences.

The general procedure for investigators reporting any adverse event is as follows:

- Report the event to Medtronic as soon as possible but no later than the timeframes outlined below. (At the time of Site Initiation, sites will be provided with the telephone and other applicable contact information of the appropriate Medtronic designee).
- Complete all sections of the Adverse Event eCRF.
- Each unique event/diagnosis must be documented separately.

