- Valve-related dysfunction requiring repeat procedure (BAV, TAVI, or SAVR)
- All-cause death

Early safety composite endpoint-incidence estimates will be provided for the two treatment groups at 30 days. The statistical method will be the Bayesian version of a comparison of proportions.

5. Incidence of Clinical Efficacy (after 30 days) at 6 months, 12 months, 18 months, 24 months and annually thereafter up to 5 years. Clinical efficacy defined as a composite of:
- All-cause mortality
  - All stroke (disabling and non-disabling)
  - Requiring hospitalizations for valve-related symptoms or worsening congestive heart failure
  - NYHA class III or IV
  - Valve-related dysfunction (mean aortic valve gradient  $\geq 20$  mmHg, EOA  $\leq 0.9$ - $1.1$   $\text{cm}^2$  and/or DVI  $< 0.35$  m/s, AND/OR moderate or severe prosthetic valve regurgitation\*)

Clinical efficacy estimates will be provided for the two treatment groups at 6 months, 12 months, 18 months, 24 months and annually thereafter up to 5 years. The statistical method will be the Bayesian version of a comparison of proportions (with predictions).

\*Refers to VARC-2 definitions

6. Incidence of Time-Related Safety at 30 days, 6 months, 12 months, 18 months, 24 months and annually thereafter up to 5 years. Time-Related Safety defined as a composite of:
- Structural valve deterioration:
    - Valve-related dysfunction (mean aortic valve gradient  $\geq 20$  mmHg, EOA  $\leq 0.9$ - $1.1$   $\text{cm}^2$  and/or DVI  $< 0.35$  m/s, AND/OR moderate or severe prosthetic valve regurgitation\*)
    - Requiring repeat procedure (TAVI or SAVR)
  - Prosthetic valve endocarditis
  - Prosthetic valve thrombosis
  - Thromboembolic events (eg. stroke)
  - VARC bleeding, unless clearly unrelated to valve therapy (eg. trauma)

Time related safety composite endpoint-incidence estimates will be provided for the two treatment groups at 30 days, 6 months, 12 months, 18 months, 24 months and annually thereafter up to 5 years. The statistical method will be the Bayesian version of a comparison of proportions (with predictions).

\*Refers to VARC-2 definitions

7. Conduction disturbance requiring permanent pacemaker implantation at 30 days, 6 months, 12 months, 18 months, 24 months, and annually thereafter up to 5 years.

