12. Echocardiographic assessment of prosthetic valve performance at discharge, 6 months, 12 months, 24 months, and annually thereafter up to 5 years using the following measures:

- transvalvular mean gradient
- effective orifice area
- degree of prosthetic aortic valve regurgitation (including transvalvular and paravalvular)

The four echocardiographic measurements will be evaluated at discharge, 6 months, 12 months, 24 months, and annually thereafter up to 5 years. All implanted subjects undergoing echocardiography procedures will be evaluated.

Continuous measures will be evaluated using a Bayesian version of a two-sample t-test. Categorical variables will be evaluated using Bayesian version of a comparison of polytomous outcomes.

Additionally, incidence of moderate/severe aortic insufficiency at discharge will be compared between groups using the Bayesian version of a comparison of proportions.

13. Aortic valve disease related hospitalizations

The number of subjects re-hospitalized after the initial index procedure will be compared at 30 days, 6 months, 12 months, 18 months, 24 months, and annually thereafter up to 5 years.

Incidence of recurrent hospitalization will be provided at 30 days, 6 months, 12 months, 18 months, 24 months, and annually thereafter up to 5 years. The statistical method will be the Bayesian version of a comparison of proportions (with predictions).

14. Cardiovascular deaths and valve-related deaths

The number of subjects experiencing cardiovascular deaths and valve-related deaths at 30 days, 6 months, 12 months, 18 months, 24 months, and annually thereafter up to 5 years. Incidences will be compared between groups. The statistical method will be the Bayesian version of a comparison of proportions (with predictions).

15. Strokes and TIAs

The number of subjects with strokes (of any severity) and TIAs at 30 days, 6 months, 12 months, 18 months, 24 months, and annually thereafter up to 5 years. A separate analysis will be performed for each of the following:

- a composite of all strokes and TIAs
- disabling strokes only
- non-disabling strokes only
- TIAs only

The statistical method will be the Bayesian version of a comparison of proportions (with predictions).

Additionally, incidence of all strokes at 30 days or hospital discharge, whichever is longer, will be compared between groups using the Bayesian version of a comparison of proportions.

16. Peri-procedural Neurological Injury (Stroke, TIA, Encephalopathy)

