### BLEEDING EVENT

Bleeding event will be defined according to the Valve Academic Research Consortium (VARC)-2; Updated Standardized Endpoint Definitions for Transcatheter Aortic Valve Implantation (TAVI); 2012-10-09.

Life-threatening or Disabling Bleeding

 
• Fatal bleeding (BARC type 5) OR
 
• Bleeding in a critical area or organ, such as intracranial, intraspinal, intraocular, or pericardial necessitating pericardiocentesis, or intramuscular with compartment syndrome (BARC type 3b) OR
 
• Bleeding causing hypovolemic shock or severe hypotension requiring vasopressors or surgery OR
 
• Overt source of bleeding with drop in hemoglobin of <math>\geq 5</math> g/dL or whole blood or packed red blood cells (RBC) transfusion <math>\geq 4</math> units* (BARC type 3b)
 

Major Bleeding ( BARC type 3a )

 
• Overt bleeding either associated with a drop in the hemoglobin level of at least 3.0g/dL or requiring transfusion of 2-3 units of whole blood/RBC, or causing hospitalization or permanent injury or requiring surgery AND
 
• Does not meet criteria of life-threatening or disabling bleeding
 

Minor Bleeding ( BARC type 2 or 3a, depending on severity )

 
• Any bleeding worthy of clinical mention (eg. access site hematoma) that does not qualify as life-threatening, disabling or major
 

\* Given one unit of packed RBC typically will raise blood hemoglobin concentration by 1g/dL, an estimated decrease in hemoglobin will be calculated.  
BARC = Bleeding Academic Research Consortium

Life-threatening and Major bleeding events are considered to be serious.

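### After the 24-month visit the required reporting list names neither TIA nor minor bleeding, although items 6 and 15 compare endpoints containing them yearly to 5 years, so those late rates may be understated

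*Combined protocol and SAP*

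**What the plan says.** Section C.5.2 sets two regimes. Up to month 24, capture is complete: "All new or worsening (from baseline) adverse events and technical observations will be captured on the AE eCRF through the 24-month follow-up visit". After that it narrows: "Once a subject has completed their 24-month scheduled follow-up visit only serious adverse events, major adverse events, cardiovascular events", then device-related events and unanticipated device effects, and finally "all strokes (CVAs) and deaths will be required to be reported". Table 3 footnote 10 repeats the list for the 3 to 5 year visits as "SAE, MAE, cardiovascular events, device-related events, including device-related technical observations, UADEs, USADEs, all stroke (CVAs), and death reports". Section C.4.9.7 refers the yearly adverse event review back to C.5.2.

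Two secondary endpoints in C.6.8.1 are compared between arms beyond month 24:

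- Item 15: "The number of subjects with strokes (of any severity) and TIAs at 30 days, 6 months, 12 months, 18 months, 24 months, and annually thereafter". The yearly counts run to year 5. TIAs alone, and strokes and TIAs combined, are separate analyses.
- Item 6, Time-Related Safety, yearly to 5 years. Its bleeding component is given as "VARC bleeding, unless clearly unrelated to valve therapy (eg. trauma", with no severity grade.

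The bleeding definition in O.2 has a minor grade: "Any bleeding worthy of clinical mention (eg. access site hematoma) that does not qualify as life-threatening, disabling or major". The MAE list in C.5.1.4 takes in only "Life-threatening, disabling or major bleeding".

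**The concern.** An endpoint analysed to 5 years needs its component events collected to 5 years. Here the collection rule changes at the 24-month visit and the analysis does not. If sites follow the list literally, some events that count toward items 6 and 15 need not be entered from then on. The cumulative incidence would flatten at about month 24 for a reason unrelated to patients.

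There is also a possible imbalance. Section C.5.1.5 ties device-relatedness to the CoreValve system: valve, delivery catheter, loading system and implant procedure. A non-serious TIA or bleed attributed to the device therefore remains reportable in the TAVI arm, and the SAVR arm has no equivalent route. Treatment is not blinded (C.4.5).

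The scheduled visits do not replace event reporting for TIA. By the O.2 definition the deficit lasts under 24 hours without a new lesion on imaging, so a yearly NIHSS would not detect one that occurred between visits.

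**Working it through.** The plan states no figure on this point, so there is none to reproduce. The main check is textual.

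**Step 1. Trace each event through the list in force after 24 months.**

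| Event | Named in the list | In MACCE or MAE (C.5.1.3, C.5.1.4) | Serious by default (C.5.1.2) | Remaining route |
|---|---|---|---|---|
| Any stroke | yes | yes | disabling only | not needed |
| Life-threatening or major bleeding | through MAE | yes | yes | not needed |
| TIA | no | no | no | meets SAE criteria, is device-related, or is read as a cardiovascular event |
| Minor bleeding | no | no | no | meets SAE criteria or is device-related |

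C.5.2 sends sites to C.5.1 for definitions. Neither C.5.1 nor O.2 defines a cardiovascular event.

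**Step 2. Check the severity limit in item 6.** Item 4 (early safety) specifies life-threatening bleeding, so the protocol sets a floor where it wants one. Item 6 sets none, so a minor bleed counts unless it is clearly unrelated to valve therapy.

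**Step 3. Check the cut-off.** It is the completed visit, and C.4.9 allows 730 ± 60 days. Full capture may stop at 730 − 60 = day 670, so some 24-month counts could also be touched.

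**Step 4. Illustrate the size.** The documents give no TIA or minor-bleeding rate and no capture share, so both are assumptions. Take a constant hazard h per year and let c be the share of events still captured after 24 months. Death as a competing risk is ignored.

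- True 5-year incidence: 1 − exp(−5h)
- Observed 5-year incidence: 1 − exp(−(2h + 3hc))

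For TIA at h = 1% and c = 0: 1 − exp(−0.05) = 4.88%, against 1 − exp(−0.02) = 1.98%, a loss of 2.90 points. The loss is zero in every row when c = 1. Losses are computed before rounding.

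| Event | h per year | True 5-year % | Loss, c = 0.5 (points) | Loss, c = 0 (points) |
|---|---|---|---|---|
| TIA | 0.3% | 1.49 | 0.44 | 0.89 |
| TIA | 1% | 4.88 | 1.44 | 2.90 |
| TIA | 2% | 9.52 | 2.76 | 5.60 |
| Minor bleed as first item 6 event | 0.5% | 2.47 | 0.73 | 1.47 |
| Minor bleed as first item 6 event | 2% | 9.52 | 2.76 | 5.60 |
| Minor bleed as first item 6 event | 4% | 18.13 | 5.06 | 10.44 |

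**Step 5. Illustrate the imbalance.** Let both arms have a TIA hazard of 1% per year, with a quarter captured after 24 months under TAVI through the device-related route and none under SAVR. The observed 5-year incidences are 2.71% and 1.98%. The spurious difference is 2.71 − 1.98 = 0.73 points, against TAVI.

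**The case against.** A reader might infer that the plan drops TIA after 24 months and that the late rates will be understated by a calculable amount. With 1,200 to 1,350 subjects followed, three years, a 10% loss of person-time and a TIA rate of 0.5%, 1% or 2% per year, the product (for example 1,200 × 3 × 0.9 × 0.005 = 16) gives 16–18, 32–36 or 65–73 unreported TIAs. The head count is plausible: the planning figures in C.6.5.2 give 1600 × 0.85 × 0.94 ≈ 1,278. The documents still do not support that reading, for these reasons:

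- Cardiovascular events stay on the list. The O.2 mortality definition treats deaths from neurological events as cardiovascular, so a site could report TIA under that term.
- Naming strokes separately does not show that the term excludes cerebrovascular events. Stroke is already in MAE through MACCE, and deaths are also listed twice over; the list is simply redundant.
- C.4.11 requires extra NIHSS examinations after a new TIA and sets no 24-month limit. This is not a reporting rule, but it means late TIAs are still to be worked up.
- Serious and device-related events remain reportable. The counts above assume none is captured by any route, and they count events whereas item 15 counts subjects. They are an upper bound with a floor of zero.
- Item 6 excludes bleeding clearly unrelated to valve therapy. If each subject counts once, it loses only those whose first qualifying event is an unreported minor bleed.
- Randomization is stratified by site, so differences in sites' reporting habits largely balance across arms.
- The text reviewed is one part of a four-part document. The case report forms and the CEC charter are not in it and might define the terms.

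All of this stands, and it limits the TIA limb to an ambiguity. It does not close the bleeding gap, because a non-serious, non-device-related minor bleed still has no clear route. Site stratification also does not offset a reporting category that exists in one arm only. The broad reading of cardiovascular events is not secure either: the protocol elsewhere pairs cardiovascular with cerebrovascular as distinct terms (MACCE) and gives neurological event its own definition.

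**Conclusion.** The mismatch between collection and analysis is real. For minor bleeding in item 6 the gap is clear on the text. For TIA in item 15 it is an undefined term that sites must interpret. The 3 to 5 year rates for these endpoints may be understated, and capture may differ by arm through the device-related route.

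The size cannot be fixed from the documents. It runs from zero, if every relevant event is captured by another route, to the right-hand column of the table if none is. Those values rest on assumed hazards, a constant rate and no competing risk.

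The consequence is limited to the late secondary comparisons, with a possible small effect on 24-month counts when the visit falls early. The primary endpoint is unaffected: deaths and all strokes stay reportable. No labeling-claim test in C.6.10.1 uses TIA, item 6 or data beyond 24 months. The point merits correction but does not threaten the trial's main conclusion.

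**What to change.** In C.5.2 and Table 3 footnote 10, add TIA and all VARC bleeding events, in both arms and regardless of seriousness or device-relatedness, to the events reported through 5 years. This also removes the dependence on the date of the 24-month visit.

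If the sponsor does not want late minor bleeding, the alternative is to state that cardiovascular events include TIA, and to restrict the bleeding component of item 6 after 24 months to life-threatening, disabling and major bleeding. The late item 6 results should then be labelled as using the narrower definition.

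The cost is a change to one sentence and one footnote (plus item 6 under the alternative), made through the amendment and approval process in Section N. The first option adds a small reporting load for sites in years 3 to 5. It uses the existing adverse event form and the yearly adverse event review in C.4.9.7.

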#### C.5.2.1 Serious Adverse Events (SAEs)

The Investigator shall notify the sponsor immediately but not later than within 3 calendar days of first learning of any SAE using the EDC system [MEDDEV 2.7/3]. If necessary, the Investigator may be requested to provide copies of source documentation regarding the event (eg., physician/nurse notes or summaries). The Investigator should also notify their IRB/MEC and, if applicable, local regulatory agencies, per their requirements.

Medtronic will conduct an evaluation of the event and if it is determined by Medtronic to be a UADE or USADE, it will be reported as described in the following sections.

#### C.5.2.2 Serious Adverse Device Effects

The Investigator shall notify the sponsor immediately, but not later than within 3 calendar days of the first learning of any SADE.

#### C.5.2.3 Unanticipated Adverse Device Effects (UADE or USADE)

Investigators must report any (potential) unanticipated adverse device effects, or unanticipated serious device effects, to Medtronic and their IRB/MEC immediately but no later than 3 calendar days after first learning of the event [MEDDEV 2.7/3]. UADEs and USADEs should be reported immediately to Medtronic via telephone as well as on an eCRF. The Investigator should also notify their IRB/MEC and, if applicable, local regulatory agencies, per their requirements.

The Investigator should consider the device labeling and the Risk/Benefit Analysis section of this document (Section D) when determining whether an event is unanticipated or not.

If an event is determined by Medtronic to be a UADE or USADE, Medtronic will report the event to all investigators to enable reporting to their respective IRB/MECs. Medtronic will provide this notification within 10 working days after Medtronic first receives notice of the effect. [21 CFR 812.150]

If Medtronic and the DSMB determine that the event presents an unreasonable risk to the participating subjects, Medtronic must terminate all investigations or parts of investigations presenting the risk in the clinical trial 5 working days after making that determination and not later than 15 working days after Medtronic first receives notice of the effect. [21 CFR 812.46] Follow-up visits for enrolled subjects will continue according the schedule of assessments.

#### C.5.2.4 Device Deficiencies and Technical Observations

Device Deficiency information and Technical Observations will be collected throughout the trial and reported to Medtronic.

Device Deficiencies and Technical Observations should be reported on an Adverse Event eCRF.

Device deficiencies that did not lead to an Adverse Event but could have led to an SADE:

- a) if either suitable action had not been taken,
- b) if intervention had not been made, or
- c) if circumstances had been less fortunate,

require immediate reporting (see **Table 6**). Initial reporting may be done on the eCRF completing as much information as is available. The original completed eCRF must be submitted to Medtronic as soon as possible.

#### C.5.2.5 All Other Adverse Events

The Investigator shall notify the sponsor within 15 calendar days of first learning of any other AE using the EDC system. If necessary, the Investigator may be requested to provide copies of source documentation regarding the event (eg., physician/nurse notes or summaries).

#### C.5.2.6 Anticipated Adverse Events

Potential risks associated with TAVI device or its components may include, but are not limited to, the following:

- Death
- Cardiac arrest
- Coronary occlusion, obstruction, or vessel spasm (including acute coronary closure)
- Emergent surgery (eg., coronary artery bypass, heart valve replacement, valve explant)
- Multi-organ failure
- Heart failure
- Myocardial infarction
- Cardiogenic shock
- Respiratory insufficiency or respiratory failure

- Cardiovascular injury (including rupture, perforation, or dissection of vessels, ventricle, myocardium, or valvular structures that may require intervention)
- Perforation of the myocardium or a vessel
- Ascending aorta trauma
- Cardiac tamponade
- Cardiac failure or low cardiac output
- Prosthetic valve dysfunction including, but not limited to:
  - Fracture
  - Bending (out-of-round configuration) of the valve frame
  - Under-expansion of the valve frame
  - Calcification
  - Pannus, (wear, tear, prolapse, or retraction in the valve leaflets)
  - Poor valve coaptation
  - Suture breaks or disruption
  - Leaks
  - Mal-sizing (prosthesis-patient mismatch)
  - Malposition (either too high or too low)/malplacement
  - Regurgitation, stenosis
- Thrombosis/embolus (including valve thrombosis)
- Valve migration/valve embolization
- Ancillary device embolization
- Emergent percutaneous coronary intervention (PCI)
- Emergent balloon valvuloplasty
- Major or minor bleeding that may or may not require transfusion or intervention (including life-threatening or disabling bleeding)
- Allergic reaction to antiplatelet agents, contrast medium, or anesthesia
- Infection (including septicemia and endocarditis)
- Stroke, TIA, or other neurological deficits
- Permanent disability
- Renal insufficiency or renal failure (including acute kidney injury)
- Mitral valve regurgitation or injury
- Tissue erosion
- Vascular access related complications (eg., dissection, perforation, pain, bleeding, hematoma, pseudoaneurysm, irreversible nerve injury, compartment syndrome, arteriovenous fistula, stenosis)
- Conduction system disturbances (eg., atrioventricular node block, left-bundle branch block, asystole), which may require a permanent pacemaker
- Cardiac arrhythmias
- Encephalopathy
- Pulmonary edema
- Pericardial effusion
- Pleural effusion
- Myocardial ischemia
- Peripheral ischemia
- Bowel ischemia
- Heart murmur
- Hemolysis
- Cerebral infarction-asymptomatic
- Non-emergent reoperation
- Inflammation
- Fever
- Hypotension or hypertension

- Syncope
- Dyspnea
- Anemia
- Angina
- Abnormal lab values (including electrolyte imbalance)
- Exposure to radiation through fluoroscopy and angiography
- Delivery catheter malfunction resulting in need for additional re-crossing of the aortic valve and prolonged procedural time

